10.1 Software

All analyses will be done using Stata version 12. Some analyses and graphs will be done in Rproject and Microsoft Office Excel.

10.2 Preparing morbidity data for analysis

Using the weekly morbidity form (Form 18, table) morbidity variables were split to create a new dataset for each morbidity symptom. I created new variables for total days with symptoms and total follow up days in each dataset which were used to calculate prevalence of each morbidity symptom per child. Mean longitudinal prevalences for each group were derived from the individual prevalences. I created morbidity episodes from a combination of symptoms by merging the datasets of self-reported symptoms. Incidences in a group were calculated as the sum of events/episodes across individuals divided by sum of follow-up times across individuals. Preparation of these data was done using STATA and detailed steps taken in preparation of these data were recorded in a STATA do file

10.3 Confidence intervals

The confidence intervals at 95% level (95% CI) will be provided for all the outcomes. I will use log-binomial regression to derive the confidence intervals for SAE risk ratio, geometric means ratio to derive the confidence intervals for mean longitudinal prevalence and negative binomial regression to derive the confidence intervals for incidence of nonscheduled visit and self-reported disease episodes.

10.4 Interaction and effect modification

The tests for interaction will include all variables that could logically modify the effect of nutrition intervention on morbidity. The following variables will be used to test the interactions:

- a. Child length for age z-score, weight for age z-score and weight for length z-score at baseline
- b. Child sex
- c. Maternal education and marital status
- d. Proxy for hygiene/water quality
- e. Iron status at baseline
- f. Anaemia status at baseline
- g. Household food insecurity access (HFIA)
- h. Seasonality

10.5 Covariate adjustment

The main analysis will be completed and shown in figures and tables without any covariate adjustment.

As a secondary analysis, generalised linear modelling (log-binomial family) will be used to model the possible predictors of SAEs. Least squares regression will be used to model the percentage of days with self-reported morbidity symptoms. Negative binomial regression will be used to model the predictors of non-scheduled visits and disease episodes. Fixed effects will be used to model for age (grouped in 2 age bands) and seasonal variation. All variables which show a statistically significant association with any of the outcomes (at p<0.05) will be included in the regression models. The covariates to be included in the models will be derived from the list below:

- a. Child length for age z-score, weight for age z-score and weight for length z-score at baseline
- b. Child sex
- c. Maternal education and marital status
- d. Proxy for hygiene/water quality
- e. Iron status at baseline
- f. Anaemia status at baseline
- g. Household food insecurity access (HFIA)
- h. Seasonality
- i. Age (divided into two bands: <12 months and >12 months)

11 References

Kathryn G. Dewey and Lacey M. Baldiviez. Safety of Universal Provision of Iron through Home Fortification of Complementary Foods in Malaria-Endemic Areas. *Adv. Nutr* 2012;**3**:555–559.



US Food and Drug Administration. Reporting Serious Problems to FDA. http://www.fda.gov/safety/medwatch/howtoreport/ucm053087.htm. (Accessed on 10th April 2014).

12 Legends to figures

Figure 1: Participant flow in CONSORT recommended format

Figure 2: Cumulative incidence curve for mortality

Figure 3: Graph of non-inferiority, comparing the risk ratios/incidence rate ratios of SAEs, non-scheduled events and care-giver reported morbidity between intervention and control group.

13 Tables

TABLE 1:

Baseline characteristics

Variable	Control	10g	20g	40g	Test
Number of participants	XXX	XXX	XXX	XXX	-
Mean (SD) age, months	xx.x (x.x)	xx.x (x.x)	xx.x (x.x)	xx.x (x.x)	ANOVA
Proportion of boys	xx.x%	xx.x%	xx.x%	XX.X%	χ^2
Mean (SD) HAZ-score	xx.x (x.x)	xx.x (x.x)	xx.x (x.x)	xx.x (x.x)	ANOVA
Mean (SD) WAZ-score	xx.x (x.x)	xx.x (x.x)	xx.x (x.x)	xx.x (x.x)	ANOVA
Mean (SD) WHZ-score	xx.x (x.x)	xx.x (x.x)	xx.x (x.x)	xx.x (x.x)	ANOVA
Mean (SD) haemoglobin, g/L	xxx (x.x)	xxx (x.x)	xxx (x.x)	xxx (x.x)	ANOVA
Proportion with anemia	xx.x%	XX.X%	XX.X%	XX.X%	χ^2
Proportion with iron deficiency	xx.x%	xx.x%	xx.x%	XX.X%	χ^2
Proportion with positive malaria RDT	xx.x%	XX.X%	XX.X%	XX.X%	χ^2

TABLE 2

Risk of SAEs by intervention group

	Results by study group				Comparison between the groups Risk ratio (95% CI)			
Variable	Control	10g LNS	20g LNS	40g LNS	10g LNS vs	20g LNS vs	40g LNS vs	
					control	control	control	
Number of participants	XXX	XXX	XXX	XXX	-	-	-	
Number of SAEs	XXX	XXX	XXX	XXX	-	-	-	
Number (%) of children who experienced any SAE	xxx (%)	xxx (%)	xxx (%)	xxx (%)	x.xx (xx to xx)	x.xx (xx to xx)	x.xx (xx to xx)	
Number (%) of children who experienced a hospitalization	xxx (%)	xxx (%)	xxx (%)	xxx (%)	x.xx (xx to xx)	x.xx (xx to xx)	x.xx (xx to xx)	
Number (%) of children who died	xxx (%)	xxx (%)	xxx (%)	xxx (%)	x.xx (xx to xx)	x.xx (xx to xx)	x.xx (xx to xx)	

Page 15 of 17

TABLE 3

Incidence of non-scheduled visits and clinical diagnoses, by intervention group

	Incidence			Comparison between the groups			
				Incidence rate ratio (95%CI)			
Variable	Control	10g LNS	20g LNS	40g LNS	10g LNS vs	20g LNS vs	40g LNS vs
					control	control	control
Number of participants	XXX	XXX	XXX	XXX	-	-	-
Total follow up days	XXXXX	XXXXX	XXXXX	XXXXX	-	-	-
Non-scheduled visits	x.xx (xxxx)	x.xx (xxxx)	x.xx (xxxx)	x.xx (xxxx)	x.xx (xx to xx)	x.xx (xx to xx)	x.xx (xx to xx)
Gastroenteritis	x.xx (xxxx)	x.xx (xxxx)	x.xx (xxxx)	x.xx (xxxx)	x.xx (xx to xx)	x.xx (xx to xx)	x.xx (xx to xx)
Acute respiratory infections	x.xx (xxxx)	x.xx (xxxx)	x.xx (xxxx)	x.xx (xxxx)	x.xx (xx to xx)	x.xx (xx to xx)	x.xx (xx to xx)
Clinical malaria	x.xx (xxxx)	x.xx (xxxx)	x.xx (xxxx)	x.xx (xxxx)	x.xx (xx to xx)	x.xx (xx to xx)	x.xx (xx to xx)
Others	x.xx (xxxx)	x.xx (xxxx)	x.xx (xxxx)	x.xx (xxxx)	x.xx (xx to xx)	x.xx (xx to xx)	x.xx (xx to xx)

Incidence = number of events / total follow up days

Page 16 of 17

TABLE 4:

Longitudinal prevalence of self-reported common childhood morbidity symptoms

	Prevalence				Comparison between the groups Geometric means ratio (95%CI)			
Variable	Control	10g milk LNS	20g LNS	40g LNS	10g LNS v control	20g LNS v control	40g LNS vs control	
Total follow up days	xxxxx	XXXXX	XXXXX	XXXXX	-	-	-	
Any illness	XX.X%	xx.x%	XX.X%	xx.x%	x.xx (xx to xx)	x.xx (xx to xx)	x.xx (xx to xx)	
Fever	XX.X%	xx.x%	XX.X%	xx.x%	x.xx (xx to xx)	x.xx (xx to xx)	x.xx (xx to xx)	
Cough	XX.X%	xx.x%	XX.X%	xx.x%	x.xx (xx to xx)	x.xx (xx to xx)	x.xx (xx to xx)	
Vomiting	XX.X%	xx.x%	XX.X%	xx.x%	x.xx (xx to xx)	x.xx (xx to xx)	x.xx (xx to xx)	
Rapid breathing	xx.x%	xx.x%	xx.x%	xx.x%	x.xx (xx to xx)	x.xx (xx to xx)	x.xx (xx to xx)	
Difficult breathing	XX.X%	xx.x%	XX.X%	xx.x%	x.xx (xx to xx)	x.xx (xx to xx)	x.xx (xx to xx)	
Nasal discharge	XX.X%	xx.x%	xx.x%	xx.x%	x.xx (xx to xx)	x.xx (xx to xx)	x.xx (xx to xx)	
Diarrhoea	xx.x%	xx.x%	xx.x%	xx.x%	x.xx (xx to xx)	x.xx (xx to xx)	x.xx (xx to xx)	
Bloody stools	xx.x%	xx.x%	xx.x%	xx.x%	x.xx (xx to xx)	x.xx (xx to xx)	x.xx (xx to xx)	
Mucoid stools	xx.x%	xx.x%	xx.x%	xx.x%	x.xx (xx to xx)	x.xx (xx to xx)	x.xx (xx to xx)	

Longitudinal prevalence = number of days with symptom / total number of days of follow up

TABLE 5:

Incidence of self-reported disease episodes

	Incidence				Comparison between the groups			
					Incidence rate ratio (95%CI)			
Variable	Control	10g milk	20g LNS	40g LNS	10g LNS v	20g LNS v	40g LNS vs	
		LNS			control	control	control	
Total follow up days	XXXXX	XXXXX	XXXXX	XXXXX	-	-	-	
Gastroenteritis	x.xx (xxxx)	x.xx (xxxx)	x.xx (xxxx)	x.xx (xxxx)	x.xx (xx to xx)	x.xx (xx to xx)	x.xx (xx to xx)	
Acute respiratory infections	x.xx (xxxx)	x.xx (xxxx)	x.xx (xxxx)	x.xx (xxxx)	x.xx (xx to xx)	x.xx (xx to xx)	x.xx (xx to xx)	
Malaria	x.xx (xxxx)	x.xx (xxxx)	x.xx (xxxx)	x.xx (xxxx)	x.xx (xx to xx)	x.xx (xx to xx)	x.xx (xx to xx)	
Others	x.xx (xxxx)	x.xx (xxxx)	x.xx (xxxx)	x.xx (xxxx)	x.xx (xx to xx)	x.xx (xx to xx)	x.xx (xx to xx)	

Incidence = number of episodes per child / total follow up days

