where D = 0 or 1 for the 20g and 40g group, respectively, and S = 0 or 1 for the milk and milk-free LNS group, respectively. Participants who received 10g / day milk-LNS and participants who received no dietary intervention will be excluded in this model. Coefficient b_2 will indicate whether the 20g milk-LNS group differs from 20g milk-free LNS group and linear combination of coefficients b_2+b_3 (Stata's *lincom* command) will tell us whether the 40g milk-LNS group differs from 40g no-milk-LNS group. If P<0.05 for coefficient b_2 or b_2+b_3 we will reject the null hypothesis of no differences between groups and use separate groups for 20g and 40g milk and milk-free LNS groups in the subsequent analyses. If P>0.05 for coefficient b_2 or b_2+b_3 we will combine milk and milk-free LNS groups in the subsequent analyses.

Another analysis will be done to compare all the LNS groups combined against the control (no dietary intervention) group.

These analyses will primarily be based on principle of *modified* intention-to-treat. The modification is due to six participants who were accidentally allocated to a group other than the one to which they were actually randomized. For each participant, the randomization code was pre-packed and sealed in an individual envelope that was opened and used for group allocation at enrolment. For these 6 individuals, the randomizer made a recording error, i.e. s/he noted down in a data collection form an incorrect group code or wrote the code with unclear handwriting. The incorrect code was later transcribed into the computer software that was used to plan participant visits and allocate interventions. These six participants were told to belong to the erroneously recorded intervention group and they received that intervention throughout the trial – hence they will also be analyzed in that group (rather than the one written on the randomization slip). All randomized participants are eligible to be included in the analysis of that outcome.

Besides the intention to treat, per protocol analysis will be done by restricting the analysis to those consuming the supplements for at least 70% of the intervention period.

7 Time points for analyses

All the above analyses will cover the period from enrolment (when the participants are 6 months old) to the end of the intervention (when the participants are 18 months old).

8 Calculation of end-points, presentation of study findings and comparison between groups

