8.6 Incidences of common childhood infectious disease episodes

Incidence of episodes for each disease (number of episodes per child / total days of follow up per child) will be presented by intervention group. Incidence rate ratios (95% CI) will be calculated for each intervention group using the control group as the reference. Results will presented by intervention group (Table 5).

9 Hypothesis testing and statistical modelling

Risk of serious adverse events will be analysed using generalised linear modelling (log-binomial family). The Cox regression will be used in the analysis of mortality outcome. Differences in longitudinal prevalences of self-reported symptoms will be analysed and tested using least squares regression. Incidences of non-scheduled visits and morbidity episodes will be analysed using negative binomial regression.

The following is the list of the end-points and the types of modelling to be used for each endpoint:

End-p	oint	Statistical modelling		
i.	Risk of SAE	Log-binomial regression		
ii.	Longitudinal prevalence	Least squares regression		
iii.	Incidence of non-scheduled visits	Negative binomial regression		
iv.	Incidence of disease episodes	Negative binomial regression		

A set non-inferiority margin of 20% will used to test the hypotheses of no marked increase in the risk of SAEs, incidences of non-scheduled visits and morbidity episodes and prevalences of self-reported morbidity symptoms due to the intervention. An increased risk of >20% (risk ratio/incidence rate ratio >1.20) suggests a harmful effect associated with the intervention. The non-inferiority margin of 20% or an incidence difference of 20% has been used in previous

studies on nutritional supplementation and morbidity (Lemaire et al, 2011; Sazawal et al, 2006; Soofi et al, 2013).

The findings of the analysis will lead to one of the following four possible conclusions:

- i. If the upper bound of the 95% CI for the risk ratio/incidence rate ratio is <1.20, a conclusion of non-inferiority will be made.
- ii. If the lower bound of the 95% CI for the risk ratio/incidence rate ratio is >1.20, a conclusion of inferiority will be made.
- iii. If the upper bound of the 95% CI for the risk ratio/incidence rate ratio is <1.00, superiority will be confirmed (suggesting a beneficial effect).

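### Appendix 8's secondary adjusted morbidity models include an age band that changes within nearly every child, but provide nothing for the within-child correlation this creates

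*SAP*

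**What the plan says.** Section 10.5 of Appendix 8 separates two layers of analysis. For the first: "The main analysis will be completed and shown in figures and tables without any covariate adjustment". The second is a secondary, adjusted analysis. For visits and episodes, "Negative binomial regression will be used to model the predictors of non-scheduled visits and disease episodes"; for symptoms, "Least squares regression will be used to model the percentage of days with self-reported morbidity symptoms". Into these models go age and season: "Fixed effects will be used to model for age (grouped in 2 age bands) and seasonal variation". Item i of the covariate list defines the first of these: "Age (divided into two bands: <12 months and >12 months". Covariates are kept if they are associated with any outcome at p<0.05.

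On follow-up, section 7 of the appendix states: "All the above analyses will cover the period from enrolment (when the participants are 6 months old) to the end of the intervention", which is at 18 months of age.

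The outcomes are described at child level. Section 10.2 speaks of day counts "which were used to calculate prevalence of each morbidity symptom per child", and section 8.6 of "Incidence of episodes for each disease (number of episodes per child / total days of follow up per child" (days in the denominator). Section 8.3 counts each participant once for the risk of serious adverse events (SAEs).

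Appendix 8 mentions no child random effect, GEE or clustered variance. Appendix 7, added on the same date, specifies mixed models with a random intercept and slope for its two interviews per participant.

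**The concern.** Randomisation is by child, and intervention group is constant over a child's whole follow-up. So are the other child-level predictors, such as sex, maternal education and baseline anaemia. Age band is not. It describes a stretch of follow-up, and a child who stays in the study contributes to both bands.

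If follow-up is split so that the term can be fitted, two records from one child are treated as if they came from two children. The negative binomial dispersion parameter allows for extra variation in each record, but not for the resemblance between records of the same child. Least squares has the same gap. Standard errors for anything constant within a child are then too small. A p<0.05 screen run on the split records would also admit child-level covariates too readily.

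At stake are the adjusted group comparisons and the list of predictors in a safety appendix, where intervals that are too narrow make the results look more certain than they are.

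**Working it through.** **Can age band be a child-level covariate?** Appendix 5 gives enrolment at 5.5 to 6.5 months of age, and Appendix 8 follows children to 18 months. Age at entry is below 12 months for every child. Age at exit is above 12 months for every child except early drop-outs. With one record per child the term is therefore either constant or a marker of early loss. The only useful fit has at least two records per child. The fixed effects named are for age and season, not for the child, so they do not remove the correlation.

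**Effect on the standard error.** The plan states no standard error, power or within-child correlation for these outcomes, so there is no figure of its own to reproduce. Take m equally weighted records per child with correlation ρ (assumed). For a predictor that is constant within the child:

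- true SE / naive SE = √(1+(m−1)ρ)
- actual two-sided error at nominal 5% = 2·[1−Φ(1.96/√(1+(m−1)ρ))]

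With m = 2:

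| ρ (assumed) | SE ratio | two-sided error |
|---|---|---|
| 0.2 | √1.2 = 1.095 | 7.4% |
| 0.3 | √1.3 = 1.140 | 8.6% |
| 0.5 | √1.5 = 1.225 | 11.0% |
| 0.7 | √1.7 = 1.304 | 13.3% |

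If season were also split within the child, m would rise. With m = 4 the SE ratio is 1.14 at ρ = 0.1 and 1.76 at ρ = 0.7.

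**Simulation with negative binomial counts.** Inputs: 322 children per arm (1932/6, assuming equal groups), two age-band records per child, a gamma frailty shared within the child (variance 0.3, 0.5, 0.5), first-band means of 1, 2 and 4 episodes with the second band at 0.8 times that, and 2000 trials per setting. Frailties and means are assumed. The count correlations were 0.21, 0.47 and 0.64. False-positive rates at nominal 5% were:

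- naive: 6.8%, 11.0%, 13.0%
- child-clustered: 4.5%, 5.2%, 5.6%

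This agrees with the formula.

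**Separate simulation with a child-level comparator** (two records, 5 episodes per child in all, frailty variance 0.5, true rate ratio 1.20, 300 runs):

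- naive mean SE 0.052
- observed SD of the estimate 0.065
- child-clustered mean SE 0.065
- mean SE from one record per child 0.065

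The naive model understates the SE by a factor of 0.0653/0.0518 = 1.26. Clustering restores the precision of the child-level analysis.

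**The case against.** The strongest reply is that the fault is not written down. Appendix 8 never says that follow-up is split or that records are treated as independent, and its outcome descriptions are per child. That is correct: the split is inferred. But no other workable reading of the age term is apparent. Kept at one record per child, section 10.5 cannot be run meaningfully. Split, it has no stated variance method. Both cases call for the same repair.

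A reader might go further and infer that the trial's safety evidence is overstated, or that LNS would be declared non-inferior too often. The document does not support either. The main results in tables and figures are unadjusted with one value per child, and that includes Figure 3, the non-inferiority graph. The 1.20 and 1.00 rules stand in section 9 and are not tied to the adjusted models, which 10.5 calls secondary and describes largely as models of predictors. SAE risk is counted once per child, so its log-binomial model is not shown to have repeated records.

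Season is also open. Appendix 4 uses season of birth and season of enrolment, which are child-level. If Appendix 8 means something similar, season needs no splitting. The argument rests on age band alone.

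Finally, the size depends on an assumed correlation. At 0.2 to 0.3 the inflation is modest.

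**Conclusion.** The point holds for the secondary adjusted models of non-scheduled visits, disease episodes and symptom days. Age band forces at least two records per child, and the named regressions do nothing about their correlation. Intervals for group and other child-level predictors would be too narrow and their p-values too small. With two records, two-sided error would be about 7% at a within-child correlation of 0.2 and 13% at 0.7, against a nominal 5%. Those figures rest on the assumed correlation, on equal weighting of records, and on the inference that follow-up is split. More records per child would raise them. The unadjusted conclusions stand as planned.

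**What to change.** In Appendix 8, section 10.5:

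- State that models with age band use one record per child per band, with log follow-up days as offset for counts. Assign age exactly 12 months to a band, since the bands as written leave it out.
- Use standard errors clustered on the child (Stata `vce(cluster id)`) or a child random intercept.
- Screen child-level covariates on one record per child, or with the same clustered variance.
- Define seasonality. If it varies within the child, apply the same clustering in 10.4 (effect modification) and 10.5.

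This costs a few sentences and one option in the Stata commands, with no new data. Relative to the naive fit, adjusted intervals widen by about 10% at a correlation of 0.2 (√1.2) and 22% at 0.5 (√1.5).
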